- The fibrosis progression rate is highly variable among patients with chronic hepatitis C. Overall it is estimated that only about 20% of patients with chronic hepatitis C will progress to cirrhosis after 20 years of infection¹. Previously identified clinical risk factors for fibrosis progression include male gender, excessive alcohol use, older age at the time of infection and the presence of steatosis on liver biopsy². However, many patients with these characteristics have mild disease and some patients without these factors have cirrhosis³.
- Besides clinical factors, recent studies suggested that host genetic factors, such as single nucleotide polymorphisms (SNPs) could play an important role in determining the risk for fibrosis progression^{4,5}.
- In the past 5 years, Celera Diagnostics has worked with 5 major academic centers in the US and enrolled 1,468 patients (984 Caucasians, 293 African Americans and 191 other races) with chronic hepatitis C (CHC). From a functional genomic scan of 25,000 SNPs, 361 SNPs were selected for the signature building based on their significant association with fibrosis risk in two large cohorts⁵. Using a 'machine learning' approach, a signature consisting of 7 markers most predictive of cirrhosis risk in Caucasian patients was developed, and Cirrhosis-Risk-Score (CRS) was calculated to determine the risk for each patient.
- The area-under-the-ROC-curves (AUROC) of the CRS in Caucasian patients was 0.75 in the Training cohort. In the Validation cohort, AUROC was only 0.53 for clinical risk factors, increased to 0.73 for CRS, and to 0.76 when CRS was combined with clinical risk factors. A CRS low-cutoff of <0.50 to identify low-risk patients would misclassify only 10.3% of high-risk patients, while a high-cutoff of >0.73 to identify high-risk patients would misclassify 22.3% of low-risk patients (Table 1).

Table 1: Predictive Values of CRS

5A. Training Cohort

CRS	All Patients	Low-Risk (Stage 0) (N=157)	High-Risk (Stage 3-4) (N=263)	NPV	PPV	Sensitivity	Specificity	Misclassifying Rate ^a
< 0.10	4 (1.0%)	4	0	100.0%		100.0%	2.5%	0.0%
< 0.20	18 (4.3%)	16	2	88.9%		99.2%	10.2%	0.8%
< 0.30	30 (7.1%)	27	3	90.0%		98.9%	17.2%	1.1%
< 0.40	55 (13.1%)	46	9	83.6%		96.6%	29.3%	3.4%
< 0.50 ^b	98 (23.3%)	71	27	72.4%		89.7%	45.2%	10.3%
> 0.70 ^b	194 (46.2%)	35	158		81.4%	60.1%	77.7%	22.3%
> 0.75	155 (36.9%)	28	127		81.9%	48.3%	82.2%	17.8%
> 0.80	67 (16.0%)	11	56		83.6%	21.3%	93.0%	7.0%
> 0.85	55 (13.1%)	9	46		83.6%	17.5%	94.3%	5.7%

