> 0.90	10 (2.4%)	0	10		100.0%	3.8%	100.0%	0.0%

5B. Validation Cohort

CRS	All Patients	Low-Risk (Stage 0) (N=14)	High-Risk (Stage 3-4) (N=140)	NPV	PPV	Sensitivity	Specificity	Misclassifying Rate ^a
< 0.10	1 (0.6%)	1	0	100.0%		100.0%	7.1%	0.0%
< 0.20	5 (3.2%)	3	2	60.0%		98.6%	21.4%	1.4%
< 0.30	14 (9.1%)	6	8	42.9%		94.3%	42.9%	5.7%
< 0.40	16 (10.4%)	6	10	37.5%		92.9%	42.9%	7.1%
< 0.50 ^b	23 (14.9%)	6	17	26.1%		87.9%	42.9%	12.1%
> 0.70 ^b	78 (50.6%)	3	75		96.2%	53.6%	78.6%	21.4%
> 0.75	57 (37.0%)	3	54		94.7%	38.6%	78.6%	21.4%
> 0.80	31 (20.1%)	1	30		96.8%	21.4%	92.9%	7.1%
> 0.85	26 (16.9%)	1	25		96.2%	17.9%	92.9%	7.1%
> 0.90	4 (2.6%)	0	4		100.0%	2.9%	100.0%	0.0%

a. The low cutoff was chosen to minimize misclassification of patients at high risk of cirrhosis as being low risk

- b. Using 0.50 and 0.70, 30.5% and 34.5% patients were not classifiable in Training and Validation cohort, respectively.
- Indices derived from routinely available laboratory results have been reported to correlate with advanced fibrosis or cirrhosis on biopsies. These indices include APRI (derived from AST and platelet)⁶ and the HALT-C cirrhosis prediction index (derived from platelet, AST/ALT ratio and INR)⁷.
 - The CRS was developed with the aim to predict the risk of cirrhosis. To date, studies performed by Celera had been cross-sectional studies showing that the CRS correlated with histological cirrhosis with an AUROC of 0.73-0.75. To validate that the CRS can predict the risk of cirrhosis, Celera has embarked on a study involving multiple liver centers to recruit patients who had baseline liver biopsies at early disease stages (F0-F1) and who have undergone serial liver biopsies.
 - The CRS did not use complications of cirrhosis (eg. hepatic decompensation and HCC) as endpoints for the study. It will be interesting to determine if the genes that predict cirrhosis also predict progression to cirrhosis complications.

3. Relations to aims of HALT-C study

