- This study will include all patients who participated in the randomized phase of HALT-C as well as patients who were responders in the lead-in phase, and will include patients with bridging fibrosis as well as those with cirrhosis

Study design

- 250 ng genomic DNA from each eligible patient will be sent to Celera for genotyping

5. Methods, data usage

Required clinical data from HALT-C DCC

- A defined data set on patients who meet eligibility criteria listed in section 4 and in whom DNA samples are available will be created by NERI and sent to Celera for analysis. The dataset will include:
 - (a) Demographics, duration of HCV infection, alcohol and smoking history, BMI, HCV genotype
 - (b) Baseline information: histology (inflammation, fibrosis and steatosis score, length of biopsy and fragmentation), baseline labs (CBC, liver panel, INR, HCV RNA), baseline ultrasound finding (spleen size), (W24 or R00) EGD findings (presence or absence of varices/portal gastropathy)
 - (c) M24 labs (CBC, liver panel, INR), ultrasound finding (spleen size) and histology (inflammation, fibrosis and steatosis score, length of biopsy and fragmentation)
 - (d) M48 labs (CBC, liver panel, INR), ultrasound finding (spleen size), histology (inflammation, fibrosis and steatosis score, length of biopsy and fragmentation) and EGD findings (presence or absence of varices/portal gastropathy)
 - (e) Occurrence of clinical outcomes
- DNA samples and dataset will be de-identified and coded using subject number only.

Genotyping

- CRS Multiplex Research Prototype: A single tube multiplex PCR-Oligonucleotide Ligation research assay (PCR-OLA) was established to genotype all 7 SNPs in CRS signature plus gender. Each of the eight distinct amplicons is genotyped by an OLA which involves the joining of an Allele-Specific Oligonucleotide containing a complementary sequence tag for a specific oligonucleotide-conjugated Luminex® bead with a Ligation-Specific Oligonucleotide containing a 3' biotin. The ligation products are then hybridized to derivatized Luminex® beads, labeled by the reporter molecule Streptavidin-Phycoerythrin, and analyzed on a Luminex® 100™ system. Genotypes are determined automatically by generic research software that compares the ratio of fluorescent signals between the two alleles.

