- Allele Specific PCR: If additional SNPs needed to be genotyped, allele specific PCR will be used. For each SNP, two amplification reactions will be performed, one for each allele. Each PCR reaction contains one of the two allele-specific primers and a common reverse primer. All reactions will be amplified on Applied Biosystems PRISM 7900HT Sequence Detection instrument. For individual DNA, the genotypes will be automatically called by a custom-designed algorithm.

Data analyses

For all the following analyses, CRS value will be calculated using a Naïve Bayes algorithm developed by Celera (see details below). The performance of CRS in HALT-C patients will be evaluated by statistical parameters such as Area under the ROC Curve (AUC), sensitivity, specificity, positive predictive value (PPV), negative predictive value (NPV) etc.

- Stage 1A: Validate the current Caucasian CRS with 7 SNPs plus gender in Caucasian and African American patients from HALT-C trial in predicting
 - Cirrhosis on baseline biopsy
 - Progression to cirrhosis on M24 or M48 biopsy – for those who did not have cirrhosis on baseline biopsy
- Stage 1B: Explore the current Caucasian CRS with 7 SNPs plus gender in Caucasian and African American patients from HALT-C trial in predicting
 - Progression to cirrhosis complications – hepatic decompensation and/or HCC
- Stage 2: Validate the optimized Caucasian CRS (upon availability) in Caucasian and African American patients from HALT-C trial. Celera is performing fine density mapping of CRS signature, in which over 600 SNPs around the original 7 SNPs are being evaluated. These SNPs will be incorporated into the modeling process to obtain a more optimized Caucasian CRS signature. The optimized Caucasian CRS is expected to be available by June 2007.
- Stage 3: Validate the African American CRS (upon availability) in African American patients from HALT-C trial. Currently, Celera has DNA samples from 293 African American (AA) patients enrolled using the same criteria as Caucasian patients. Celera is in the process of identifying SNPs significant in AA population from the genome scan data. Although sample size may be inadequate, Celera will explore the possibility of building the AA CRS signature. The preliminary result is expected to be available in August 2007. If a predictive signature can be identified, its performance will be validated in AA patients from HALT-C trial.

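### Stage 1A judges the CRS for progression to cirrhosis without using the collected baseline histology as a comparator, so a crude AUC above 0.50 cannot by itself show prediction beyond present stage.

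*Protocol*

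**What the plan says.** In Protocol section 5 (Data analyses), the second Stage 1A item is "Progression to cirrhosis on M24 or M48 biopsy", and it applies only "for those who did not have cirrhosis on baseline biopsy". Performance is to be "evaluated by statistical parameters such as Area under the ROC Curve (AUC), sensitivity, specificity", PPV and NPV; the list is left open.

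Section 5, item (b) of the required clinical data, puts the baseline scores in the analysis data set: "Baseline information: histology (inflammation, fibrosis and steatosis score, length of biopsy and fragmentation". In the progression item, baseline histology serves only to exclude cirrhosis.

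Stage 4 is the only combination analysis described. It joins the CRS to age or duration of infection and to a laboratory-based index, and its stated target is cirrhosis. It names neither the baseline fibrosis score nor progression.

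Section 1 makes accuracy for progression from advanced fibrosis to cirrhosis part of the first primary aim. On the evidence so far, section 2 says that "studies performed by Celera had been cross-sectional studies showing that the CRS correlated with histological cirrhosis". On the cohort, section 4 says that the study "will include patients with bridging fibrosis as well as those with cirrhosis".

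**The concern.** The endpoint is reaching a fixed threshold, not change in the fibrosis score, so a patient who starts closer to the threshold has less distance to cover. The CRS was trained to distinguish stages at one point in time. If it also tracks fibrosis score among patients below the threshold, it will rank those who later cross it above those who do not, even if it says nothing about the speed of progression. The crude AUC cannot tell these two explanations apart.

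This bears on what a positive result may be taken to mean. Section 6 expects accuracy to be highest in baseline cirrhosis, then in progressors, then in non-progressors. A score that reflects only present severity could produce such a gradient. Section 3 makes a second, larger proposal depend on favourable results from this one and states no numerical threshold. Even an AUC a little above 0.50 could therefore be read as support for prediction of progression.

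**Working it through.** **1. The plan's own figure.** Table 1 (training cohort) gives counts by cut-point for 157 stage 0 and 263 stage 3-4 patients. The trapezoidal area through those cut-points is 0.751, against the stated 0.75. The prior in the Naïve Bayes formula is 263/420 = 0.626, as stated. The score is thus tied to the contrast of stage 0 with pooled stages 3-4.

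**2. Model for the crude AUC with no CRS effect on progression.** Split the non-cirrhotic group into a lower and a higher baseline fibrosis level. Let
- s = share at the higher level,
- pL, pH = progression risk at the lower and higher level,
- A = AUC with which the CRS separates the two levels.

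Within a level the CRS has no effect. By Bayes' rule:
- P = s·pH + (1−s)·pL
- share at the higher level among progressors: a = s·pH / P
- share at the higher level among non-progressors: b = s·(1−pH) / (1−P)
- crude AUC of the CRS = 0.5 + (a−b)(A−0.5)
- AUC of the baseline level alone = 0.5 + (a−b)/2

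The AUC within a level is 0.50 by construction.

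**3. Assumed inputs (none is in the documents):** s 30-40%, pL 10-20%, pH 40-50%, A 0.60 or 0.65.

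Smallest case (s = 0.30, pL = 0.20, pH = 0.40):
- P = 0.12 + 0.14 = 0.26
- a = 0.12/0.26 = 0.4615; b = 0.18/0.74 = 0.2432; a−b = 0.2183
- A = 0.60: 0.5 + 0.2183 × 0.10 = 0.522
- A = 0.65: 0.5 + 0.2183 × 0.15 = 0.533
- baseline level alone: 0.5 + 0.2183/2 = 0.609

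Largest case (s = 0.40, pL = 0.10, pH = 0.50):
- P = 0.20 + 0.06 = 0.26
- a = 0.20/0.26 = 0.7692; b = 0.20/0.74 = 0.2703; a−b = 0.4990
- A = 0.60: 0.550
- A = 0.65: 0.575
- baseline level alone: 0.749

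Over all combinations:

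| Quantity | Range |
|---|---|
| Crude AUC of CRS, A = 0.60 | 0.522-0.550 |
| Crude AUC of CRS, A = 0.65 | 0.533-0.575 |
| Baseline level alone | 0.61-0.75 |

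**4. Anchoring A to the plan's AUC.** For two normal distributions of equal variance, AUC 0.75 is a shift of √2·Φ⁻¹(0.75) = 0.954 SD between stage 0 and stages 3-4. Taking the pooled group as stage 3.5 and spreading the shift linearly gives 0.954/3.5 = 0.27 SD per stage, so A = Φ(0.27/√2) = 0.576. Then:
- inputs of step 3: 0.5 + 0.2183 × 0.076 = 0.517 to 0.5 + 0.4990 × 0.076 = 0.538;
- wider inputs (s 30-50%; pL/pH from 20%/30% to 10%/60%): 0.509-0.543;
- half a stage (0.14 SD), wider inputs: 0.505-0.521;
- one shared level (A = 0.50): exactly 0.50.

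**5. Against sampling error.** The Hanley-McNeil standard error at an assumed 400 patients is about 0.030-0.034 over the one-stage cases. The largest one-stage artefact is about 1.4 standard errors. The sample cap of 670 covers both races and cirrhotic as well as non-cirrhotic patients, so the number in this analysis is lower than 670; the Protocol does not state it.

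**The case against.** **Baseline stage is already partly conditioned on.** The analysis excludes baseline cirrhosis, and sections 4 and 6 describe the remainder as starting from bridging fibrosis. If the score has a single level there, adjusting for fibrosis changes nothing. This stands. The documents give neither the scale of the score nor its spread in this group.

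**The mechanism is not shown.** A reader might infer that high-CRS patients do start nearer to cirrhosis. Table 1 does not support that, because it pools stages 3 and 4 against stage 0 and says nothing about differences within the bridging group. Values of A of 0.60-0.65 are also generous. They correspond to 0.36-0.54 SD, or 38-57% of the whole stage 0 versus 3-4 separation, placed inside one sub-step.

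**The crude AUC answers the stated aim.** The first primary aim asks how accurately the CRS predicts progression, and the crude AUC measures that. A reader might infer that it is the wrong estimate and should be demoted. That does not follow. The value of 0.50 in the working belongs to a different quantity, prediction given baseline level. The CRS is also germline, so baseline fibrosis and inflammation may lie on the path from gene to outcome, and adjusting for them could remove part of the effect under study. This stands, and it limits the fix.

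**Detail may sit in an analysis plan.** The list of measures is open, nothing bars stratification, and an analysis plan not shown may add it. This lowers the weight of the point. It does not remove it, because the Protocol itself fixes population, endpoint and type of measure for a primary aim and names its one combination analysis without histology.

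**Conclusion.** The point holds in a limited form. As written, the progression analysis evaluates the CRS alone, and no stage sets it against the baseline fibrosis and inflammation scores that are already collected. A crude AUC above 0.50 would therefore not by itself show that the CRS predicts progression beyond present stage.

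The possible artefact is small to moderate: about 0.02 to 0.075 AUC under the assumed two-level inputs, about 0.01 to 0.04 when anchored to the plan's AUC with a one-stage spread, and none if all non-cirrhotic patients share one level. It rests on a CRS difference by fibrosis level within the non-cirrhotic group, which is assumed. The documents do not support saying that the planned AUC is invalid, that baseline stage is ignored altogether, or that baseline stage is the dominant source of outcome variation. This is a cheap improvement to what a positive result can mean, not an error that invalidates the analysis.

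**What to change.** In the Stage 1A progression item:
- Keep the crude AUC as the measure of predictive accuracy.
- Beside it, report the CRS AUC stratified by or adjusted for the baseline fibrosis score.
- Report what the CRS adds to a model with baseline fibrosis and inflammation scores, as the gain in AUC or as the CRS odds ratio with 95% CI.
- State that prediction of progression beyond present stage will be claimed only if the conditional estimate supports it.

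Cost: a short addition to the text and one extra model; every variable is already in the data set to be prepared by NERI. The result may look less favourable to the CRS. Because the conditional estimate may remove genetic effect that acts through baseline histology, it should accompany the crude AUC and not replace it.

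### The protocol does not ensure that HALT-C stays unseen for the Stage 2 and Stage 3 scores, because nothing locks them before their builder, Celera, holds HALT-C outcomes

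*Protocol*

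**What the plan says.** **The Stage 1 score exists.** Section 5, Data analyses, sets the task: "Validate the current Caucasian CRS with 7 SNPs plus gender in Caucasian and African American patients from HALT-C trial in predicting" baseline cirrhosis and later progression.

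**The Stage 2 and Stage 3 scores do not exist yet.** Stage 2 concerns an optimized Caucasian score drawn from more than 600 SNPs around the original seven, expected by June 2007: "These SNPs will be incorporated into the modeling process to obtain a more optimized Caucasian CRS signature". Stage 3 concerns an African American score with a preliminary result expected in August 2007: "Although sample size may be inadequate, Celera will explore the possibility of building the AA CRS signature". Both are to be validated in HALT-C once available.

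**Celera receives the DNA and the outcomes.** From Section 4: "250 ng genomic DNA from each eligible patient will be sent to Celera for genotyping". From Section 5, the defined data set "will be created by NERI and sent to Celera for analysis". It holds baseline, M24 and M48 histology, and its last item is "Occurrence of clinical outcomes". On coding: "DNA samples and dataset will be de-identified and coded using subject number only". That protects identity and leaves outcomes linked to genotypes. The assay covers seven SNPs plus gender, with one extension: "If additional SNPs needed to be genotyped, allele specific PCR will be used".

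**Celera also analyses.** Section 7 gives the analysis to Celera's biostatisticians, and NERI verifies the final results. The agreement in Part I gives the analysis to NERI unless the HALT-C study approves otherwise.

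**The concern.** A validation estimate is unbiased only if the score was fixed without knowledge of the cohort it is tested in. Here one party builds the scores, holds the linked genotypes and outcomes, and computes the performance. The protocol contains neither a lock on the scores nor a statement that HALT-C results stay out of their development.

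Section 6 makes the path concrete. It says that the Stage 1 result of the Caucasian score in African American patients will help decide whether a separate African American signature should be pursued. The same patients are then to validate that signature. If a SNP set, weight or cutoff were kept or dropped in the light of HALT-C results, the HALT-C AUC would partly reflect selection, and the word validation would claim more than the data support. NERI's check of final results would confirm the arithmetic but could not reveal how the score was chosen.

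The African American score, a secondary aim, and the Stage 2 score are at stake. Stage 1, which serves the primary aims, is not affected.

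**Working it through.** **Step 1. Was the Stage 1 score fixed outside HALT-C?** The score formula in Section 5 uses a prior of 0.626. Table 1 gives 263 high-risk and 157 low-risk patients in the training cohort:

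263 / (263 + 157) = 263 / 420 = 0.626.

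The plan's figure is reproduced, so the current score is anchored in Celera's own training cohort. No such anchor can be checked for the Stage 2 and Stage 3 scores. Even for the current score the cutoff is not stated once: the background text ties a 22.3% misclassification rate to a high cutoff of 0.73, while Table 1 shows 35/157 = 22.3% at 0.70. Cutoffs therefore belong in any lock.

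**Step 2. Order of events.**

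| Element | What the protocol fixes |
|---|---|
| Optimized Caucasian score | expected by June 2007 |
| African American score | preliminary result expected August 2007 |
| DNA and data transfer | no date |
| Score lock or deposit before transfer | none |
| Stated development sources | fine mapping; 293 African American patients and genome scan data, all Celera's own |
| Stated use of HALT-C | validation |

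The order of the stages suggests that outcomes could reach Celera before the new scores are final. The text neither says so nor excludes it.

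**Step 3. Size of a mild leak.** Suppose Celera has five finished scores, all worthless and mutually independent, and reports the one with the highest HALT-C AUC. The number five is an assumption. So are the cirrhosis share of 40% and the group sizes of 500 and 120; the protocol gives only a ceiling of 670 samples.

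Null standard error of the AUC, with n1 cases and n0 non-cases:

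SE = sqrt[(n1 + n0 + 1) / (12 × n1 × n0)]

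- n = 500 (200 and 300): sqrt(501 / 720,000) = 0.026
- n = 120 (48 and 72): sqrt(121 / 41,472) = 0.054

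The expected maximum of five independent standard normal values is 1.163, so the mean reported AUC is:

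- n = 500: 0.50 + 1.163 × 0.026 = 0.53
- n = 120: 0.50 + 1.163 × 0.054 = 0.56

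The chance that the chosen score exceeds the upper 2.5% limit is 1 − 0.975^5 = 11.9%.

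Simulation agrees: mean AUC 0.529 and 0.562 in one run, and 0.531 and 0.565 in another, where 11.6% and 13.4% exceeded the limit.

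**Step 4. Sensitivity to the assumptions.** With a cirrhosis share of 30% or 50%, the same formula gives 0.533 or 0.530 at n = 500, and 0.567 or 0.562 at n = 120, so the share hardly matters. The number of candidates matters more. In simulation, the best of 20 gives 0.549 (n = 500) and 0.601 (n = 120), and the best of 100 gives 0.567 and 0.636. Correlated candidates would give less.

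**Step 5. Outer bound, not a planned procedure.** If only the seven weights were re-estimated in the HALT-C patients themselves, worthless SNPs would give a mean AUC of 0.57 (n = 500) or 0.63 (n = 120). If seven SNPs were chosen from 600 independent ones in HALT-C, the figure would be about 0.66 to 0.70 at n = 500 to 670. A score locked beforehand gives 0.49 to 0.51 in that same simulation.

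**The case against.** **Nothing says that HALT-C is used for development.** This is right and limits the point. A reader might infer that Celera will build the new scores after receiving HALT-C outcomes, so that HALT-C is certainly not an unseen cohort. The documents do not support that. No transfer date is given, the named development sources are Celera's own, and Stage 3 puts the signature first and its HALT-C test second. Section 3 also moves discovery of complication scores to a separate proposal and says that new scores need external cohorts, so the authors know the distinction.

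**The extra genotyping clause proves little.** Also right. Any new SNP in a finished score must be typed in HALT-C merely to calculate the score. The clause does not describe a search for SNPs in HALT-C, so the figures in Step 5 illustrate something that is not planned. They also assume independent SNPs, whereas SNPs clustered around seven loci would inflate the AUC less.

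**The mild leak is small beside the quoted AUC of 0.73 to 0.75.** True for the AUC itself: 0.53 or 0.56 would not be mistaken for 0.73. The false-positive rate, nearly five times nominal (11.9 / 2.5 = 4.8), still matters for a claim that a score has been validated.

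**Score locking belongs in an SAP.** The details of a lock could stand there. Who holds outcomes while a model is being built is a data-flow decision, however, and Section 5 makes it. A later document cannot undo a release that has already happened.

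**Conclusion.** The point holds as a cheap improvement. The protocol leaves the Stage 2 and Stage 3 validation unprotected: the builder of unfinished scores is also to hold unmasked outcomes and run the analysis, with no lock in between. It does not show that contamination is planned or has occurred.

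The illustrated size is a mean AUC of about 0.53 (n = 500) or 0.56 (n = 120) for a worthless score, with about 12% instead of 2.5% nominally significant in the favourable direction. This rests on five independent candidates, 40% cirrhosis and assumed group sizes. If the scores are finished before Celera receives the outcomes and are not changed afterwards, the bias is zero. The protocol does not secure that condition.

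**What to change.** Add to Section 5:

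1. No HALT-C genotype or outcome data and no Stage 1 results are used to develop the Stage 2 or Stage 3 scores.
2. Each score is deposited with NERI, with a date, before Celera receives patient-level HALT-C outcomes. The deposit holds the SNP list, genotype coding, class-conditional probabilities, prior and cutoffs.
3. If outcomes are released earlier for Stage 1, NERI computes the Stage 2 and Stage 3 performance from the deposited score.
4. Any score not locked before Celera had the outcomes, or changed afterwards, is reported as exploratory or development work and not as validation. This includes scores evaluated under item 3: NERI's computation stops selection at the evaluation step but cannot show that HALT-C results did not shape the score.

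Section 7 should also say whether the approval that Part I requires for Celera's analyst role has been given.

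The cost is protocol wording, a small amount of NERI work and some sequencing of the data release. Withholding all outcomes until both scores are locked would go too far, since the African American score may never be built. Under the wording above Stages 1 and 4 need not wait for it; a score that arrives late loses only the validation label.
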